3.2 ADMINISTRATION AND DURATION OF TREATMENT

Each of the three ETBX vaccines will be administered on Weeks 0, 3, and 6 followed by booster vaccines every 8 weeks for up to a year. Treatment may be shorter for patients who experience progressive disease (unequivocal or confirmed) or unacceptable toxicity, withdraw consent, or if the Investigator feels it is no longer in their best interest to continue treatment. For specifics on drug administration see section [11.1.5](#).

Vital sign assessments (temperature, heart rate, blood pressure, respiratory rate) are to be obtained after the subject has been in a seated resting position for at least 5 minutes. For the first injection, vital signs must be assessed 30 and 60 minutes after the injection. Vital signs must be assessed 30 minutes after the subsequent injections.

3.3 DOSE DELAY OR DISCONTINUATION

Applies to events occurring outside of the DLT evaluation period

- Patients must have recovered to \leq grade 2 for injection site reaction or grade \leq 1 for any other toxicity related to the vaccines for the parameters used to assess levels of organ function required for eligibility (see Section [2](#)) after each vaccination in order to receive a subsequent vaccination. Patients will receive a diary card to record injections site reactions (see [Appendix B](#)).
If \geq grade 3 nonautoimmune toxicity attributable to the vaccines persists for $>$ 42 days, the patient will not receive further vaccine inoculations and will be removed from the protocol treatment and followed for resolution of toxicity and immune/survival endpoints.
- Patients who develop any \geq grade 3 autoimmunity, not related to a therapeutic response, will be removed from the protocol treatment and followed for resolution of toxicity and immune/survival endpoints.
- Patients who develop any grade 4 toxicity attributable to the vaccines will be removed from the protocol treatment and followed for resolution of toxicity and immune/survival endpoints.
- Dosing of the vaccines injections should be given on schedule every 3 weeks (Week 0, 3, and 6), and then bi-monthly (every 8 weeks) boosts for up to a year. In the event of conflicts, a +/- 1 week window is acceptable.
- For unrelated acute illnesses present at the time of a scheduled vaccination, dosing can be delayed until symptoms subside, or the subject may be withdrawn at the discretion of the Investigator; delays up to 4 weeks are considered acceptable in this setting.

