3.1.1 Dose Limiting Toxicity

For the purposes of dose escalation a dose limiting toxicity (DLT) is defined as:

- Any Grade 3 or greater toxicity that is possibly related to the vaccine and as defined by Common Terminology Criteria for Adverse Events (CTCAE) Version 5.0 with the exception of transient (≤ 24 hours) Grade 3 flu-like symptoms or fever, which is controlled with medical management or transient (≤ 24 hours) Grade 3 fatigue, skin reactions or rash, headache, nausea, emesis that resolves to Grade ≤ 1 or asymptomatic grade 3 amylase/lipase elevation. For purposes of dose escalation the DLT evaluation period will be for 3 weeks following the first dose of drug.

Subjects experiencing a DLT will be removed from protocol therapy.

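### Read literally, the scope line of Section 3.3 excludes the whole interval before the week-3 dose and contradicts the section's own recovery rule

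*Combined protocol and SAP*

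**What the plan says.** Section 3.3 (Dose Delay or Discontinuation) begins with a limit on its own reach: "Applies to events occurring outside of the DLT evaluation period". Its first bullet then requires recovery "after each vaccination in order to receive a subsequent vaccination". The required level is Grade 2 or less for injection site reactions. It is Grade 1 or less for other vaccine-related toxicity in the parameters that Section 2 uses to judge organ function. The same bullet mentions the diary card. A later bullet restates the weeks 0, 3 and 6 schedule and adds: "In the event of conflicts, a +/- 1 week window is acceptable".

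Section 3.1.1 fixes the period: "For purposes of dose escalation the DLT evaluation period will be for 3 weeks following the first dose of drug". With listed exceptions, a DLT is "Any Grade 3 or greater toxicity that is possibly related to the vaccine", and its consequence is stated: "Subjects experiencing a DLT will be removed from protocol therapy".

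Section 3.2 has each vaccine "administered on Weeks 0, 3, and 6 followed by booster vaccines every 8 weeks". It lets treatment be cut short for unacceptable toxicity or "if the Investigator feels it is no longer in their best interest to continue treatment".

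**The concern.** The scope line and the first bullet give different answers for dose 2. If the scope line governs, toxicity that arose after dose 1 is outside 3.3 when dose 2 falls due, and no stated grade decides whether to inject. If the bullet governs, dose 2 waits until recovery.

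Dose 2 is the first repeat exposure to a combination that Section 1.2.8 says has not been given to humans before. Section 3.4 rules out dose changes other than de-escalation, so for a subject with unresolved toxicity short of a DLT, delay is the main tool. Section 3.3 is where toxicity-driven delay is defined. What is at stake is one safety check on an individual's second dose; the dose-finding result is not.

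**Working it through.** No sample size, power or error rate bears on this point. The check is day counting and a comparison of sections.

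**1. How much of the interval is excluded.** Take dose 1 as day 0. Dose 2 is planned on day 3 × 7 = 21. The one-week window gives day 21 − 7 = 14 to day 21 + 7 = 28.

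| DLT period used | Dose 2 given on | Excluded by the scope line | Left under 3.3 |
|---|---|---|---|
| 3 weeks (3.1.1) | day 14 | all days since dose 1 | 0 days |
| 3 weeks (3.1.1) | day 21 | days 0–20; day 21 itself not specified | 0 days before the visit |
| 3 weeks (3.1.1) | day 28 | to day 21 | 28 − 21 = 7 days |
| 1 week (8.4.4) | day 21 | days 0–7 | 21 − 7 = 14 days |

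The defining section is 3.1.1, so the second row is the base case. Section 8.4.4 speaks of observing DLTs for 1 week. That is a separate inconsistency, but it would shorten the exclusion if it governed.

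**2. Whether another section supplies the missing grade.**
- 3.1.1 removes subjects with a DLT and is silent on re-dosing after lesser toxicity.
- 3.2 and 3.7.1 rest on unacceptable toxicity, unexpected serious events and investigator discretion. For the rest, 3.7.1 points back to 3.1.1 and 3.3.
- 7.6.1 provides weekly discussion of each patient, without a threshold.
- 8.4.6.2 says its halting rules are not rules for delaying one subject's schedule. Its wider power to suspend is a matter of judgement.

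None sets a grade for giving dose 2.

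**3. Which toxicities are left.**
- Possibly related Grade 3 or greater, outside the listed exceptions: a DLT, so the subject is removed.
- Excepted Grade 3 events: brief, or asymptomatic amylase or lipase rises. Neither enzyme is a Section 2 eligibility parameter, so the first bullet does not reach them anyway.
- Grade 2 injection site reaction: the first bullet already allows dosing.
- Vaccine-related Grade 2 change in a Section 2 organ-function parameter (neutrophils, hemoglobin, platelets, creatinine, bilirubin, ALT or AST): the two readings differ here.

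**4. When that change would be seen.** The calendar in 3.5 has chemistry and CBC at baseline and week 3, with none scheduled between. On schedule, a routinely found change appears at about day 21. Detecting the change before then needs an unscheduled test or an early visit.

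**5. How many decisions.** The calendar marks injections at weeks 0, 3, 6, 14, 22, 30, 38, 46 and 54: 9 visits, 9 − 1 = 8 re-dosing decisions, of which one is dose 2 (1 of 7 if week 54 is not dosed).
- No de-escalation: at most 6 + 4 = 10 dose-2 decisions, or 6 if the exclusion covers dose finding only.
- De-escalation: at most 6 − 2 = 4 at dose level 1, since at least 2 subjects have DLTs and are removed (assuming the DLTs precede dose 2). At dose level −1, at most 6 + 4 = 10, or 6 for dose finding only.

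These are ceilings on the decisions, not counts of affected subjects. The documents give no rate for the residual toxicity.

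**The case against.** The strongest reply is that 3.3 shows on its face that it was meant to reach dose 2. The first bullet covers each vaccination. The diary card it invokes records only the seven days after the first injections (3.6) and is reviewed at week 3. The scheduling bullet names week 3. The natural reading is that DLTs go to 3.1.1 and the recovery check applies before every dose. This stands as evidence of intent. It does not remove the conflict, because the scope line says otherwise without qualification.

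Three further replies narrow the point.
- The scheduled laboratory tests fall at the day-21 boundary, which 3.1.1 does not assign to either side.
- The scope line speaks of events, while the bullet tests status at dosing. Under 6.1 an abnormal laboratory value is recorded as an adverse event only if it meets listed criteria, so a silent Grade 2 value may not be an excluded event at all.
- One team at one center discusses every patient weekly, which makes divergent decisions less likely.

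All three stand. So does the point that a 1-week period under 8.4.4 would bring a week-3 finding back under 3.3. Even then the first week would be excluded, against the first bullet.

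A reader might infer that the protocol abolishes the recovery check before dose 2, or permits injection over unresolved toxicity. The documents do not support that. The scope line authorizes nothing, the section's own content points the other way, and discretion to withhold remains. Nor do they support calling the conflict clear-cut throughout days 14–21, for the boundary reason above.

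**Conclusion.** There is a real drafting conflict of minor safety importance. On the literal text, none of the interval from dose 1 to an on-schedule dose 2 falls under 3.3, and no other section supplies a re-dosing grade for toxicity short of a DLT. The likely intent is that the recovery rule covers dose 2, so exposure is confined mainly to a vaccine-related Grade 2 organ-function change present at week 3 in a subject without a DLT.

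This rests on the 3-week period in 3.1.1 and on reading the scope line by date of onset. It is also unclear whether the exclusion reaches the 4 expansion subjects, because 3.1.1 ties the period to dose escalation. No probability can be given. The nearest evidence is reassuring: 11.1.2 reports no biologically important laboratory change at week 9 among the 28 patients who completed the earlier single-vaccine regimen. The MTD count and the endpoints are not affected.

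**What to change.** Replace the scope line of 3.3 with:

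> DLTs occurring in the DLT evaluation period are handled under 3.1.1 (removal from protocol therapy). All other toxicity, whenever it occurs and in both dose finding and expansion, is handled under this section, and the recovery requirement in the first bullet applies before every vaccination after the first, including week 3.

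This keeps the present grades and parameters and needs no change to 3.1.1. It also brings the discontinuation rules into force from dose 1. That matters for autoimmunity: the 3.3 rule on Grade 3 or greater autoimmunity has no vaccine-attribution test, whereas a DLT must be possibly related. An autoimmune event judged unrelated in the first 3 weeks therefore has no specific rule if the scope line is taken literally. The new text does not settle whether expansion subjects have a DLT evaluation period, but the recovery check applies to them either way.

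The only downside is an occasional delayed second injection. No visit or test is added: the week-3 chemistry and CBC are already scheduled and need only be read before dosing.

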3.4 DOSE MODIFICATIONS

No dose modifications are allowed with these vaccines except for dose de-escalation as described in section [3.1](#).

3.5 STUDY CALENDAR

Assessment	Screening	Treatment (Every 3-Week Dosing)			Bimonthly_Boosters (Every 8-Week Dosing)						End of Treatment (within 90 days after the last vaccine) ^m	Follow Up ^l
		Baselin e/0	3	6	14	22	30	38	46	54		
Study Week	Day -28 to -1ⁿ											
Clinic Visit	X	X ^c	X	X	X	X	X	X	X	X	X	
Informed Consent	X ^a											
Inclusion/Exclusion	X											
Demographics	X											
Confirmation of diagnosis (path report)	X											
Physical Examination, Height ^b , Weight, ECOG	X ^c	X ^c	X	X	X	X	X	X	X	X	X	
Medical History ^d	X	X ^c										
Concomitant Medications	X	X ^c	X	X	X	X	X	X	X	X	X	
Vital Signs ^e	X	X ^c	X	X	X	X	X	X	X	X	X	
12-Lead ECG	X				X	X	X	X	X	X	X	
Confirm Contraceptive Measures ^f	X											
Study Drug Injection/ Injection Site Reaction Monitoring ^g		X	X	X	X	X	X	X	X	X	X	

Assessment	Screening	Treatment (Every 3-Week Dosing)			Bimonthly_Boosters (Every 8-Week Dosing)						End of Treatment (within 90 days after the last vaccine) ^m	Follow Up ^l
		Baseline e/0	3	6	14	22	30	38	46	54		
Study Week	Day -28 to -1ⁿ	Baseline e/0	3	6	14	22	30	38	46	54		
Dispensation of Subject Diary Card ^h		X										
Review of Subject Diary Card ^h			X									
Tumor Imaging ⁱ	X			X	X	X	X	X	X	X		
Pregnancy Test ^j	X ^{c,n}	X ^c	X	X	X	X	X	X	X	X	X	
Urinalysis	X ⁿ										X	
Chemistry Panel	X ^{c,n}	X ^c	X	X	X	X	X	X	X	X	X	
CBC, Differential, Platelets	X ^{c,n}	X ^c	X	X	X	X	X	X	X	X	X	
Coagulation	X ⁿ										X	
Serum Virology (HIV, HBV, HCV) ^k	X ⁿ											
Adverse Events		X	X	X	X	X	X	X	X	X	X	
Exploratory Immune Analysis		X		X	X		X				X	
Telephone Follow Up												X

^a Informed consent may be obtained on D0 after eligibility is confirmed and other screening protocols may be used to obtain screening labs and procedures as per NCI's internal SOP

^b Height will only be assessed at screening.

^c If the assessment is performed within 24 hours prior to the first dosing, a second assessment at baseline/week 0 can be omitted.

^d Complete medical history will be evaluated at screening and includes current and past cardiac and pulmonary history, documentation of diagnosis including history of current and prior cancers, prior treatment(s), and prior radiologic studies. Any new events in the medical history will be evaluated at baseline..

^e Vital signs include temperature, heart rate, blood pressure, and respiratory rate. Vital sign assessments are to be obtained after the subject has been in a seated resting position for at least 5 minutes. For the first injection, vital signs must be assessed 30 and 60 minutes after the injection. Vital signs must be assessed 30 minutes after the subsequent injections.

^f Acceptable contraceptive measures are described in Section [2.1.1.12](#).

^g Injection site reactions will be monitored

^h Subjects will be given a diary card for the self-evaluation and reporting of injection site reactions.

ⁱ All baseline tumor measurements should be performed based on the subject's qualifying scan obtained within 28 days prior to the start of treatment. Tumor imaging and assessments will be performed

^j Serum pregnancy test will be performed on females of childbearing-potential and women < 12 months since the onset of menopause. The pregnancy test will be performed at each dosing visit with the result confirmed as negative prior to dosing.

^k Serum virology test for HIV (as determined by ELISA and confirmed by western blot), and HBV and HCV (as determined by HBsAg and hepatitis C serology).

^l After the subject completes or withdraws from study therapy, the study team will contact the subject approximately every 3 months for 12 months and then approximately every 6 months for 24 months and then every 12 months thereafter for another 24 months to collect follow-up information, including survival status and any current cancer treatment regimen.

^m If the patient cannot return to the Clinical Center within 90 days after the last vaccine, the patient will be contacted by phone to AEs and laboratory assessments will be deferred until a later point if at feasible.

ⁿ See section [2.2](#) for screening criteria which are exceptions to the D-28 to D-1 screening window period.

3.6 INJECTION SITE REACTIONS

Local injection site reactions are expected to occur over several days after vaccination. Erythema and some soreness are possible. Injection site reactions will be monitored by clinic staff prior to discharge and by subject self-evaluation and reporting. Subjects will be given a diary card with reporting fields for diameter of erythema and duration for the seven days after the first set of vaccine injections (see [Appendix B](#)). In addition, pain at the injection site, fever, and chills will be collected as Yes/No and medications (over-the-counter ibuprofen, acetaminophen, aspirin, etc.) taken for injection site pain or discomfort as Yes/No. The site staff will review the diary cards with the subject during the next clinic visit and record responses in the case report form.

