Anti-Ad5 antibody (Ab) and CMI against Ad5 were correlated with CEA-specific CMI. Each patient had their serum and PBMC sample tested at baseline (prior to treatment) and at 9 weeks after completion of 3 treatments. Nineteen of 31 colorectal cancer patients (61%) tested in this study had Ad5 neutralizing activity in serum samples prior to the onset of treatment with Ad5 [E1-, E2b-]-CEA(6D). The mean pre-treatment Ad5 Ab titer value obtained among all patients was $1:189 \pm 1:71$ SEM and the mean pre-treatment Ad5 Ab titer among seropositive patients was $1:308 \pm 1:108$. Analysis of serum samples from patients who received 3 immunizations revealed Ad5 Ab titers that were significantly increased ($P < 0.0001$, *Mann-Whitney test*) by week 9 (mean $1:4767 \pm 1:1225$ SEM) when compared with their respective baseline values. Analysis of PBMC for CMI responses to Ad5 also revealed a significant increase ($P < 0.01$, *Mann-Whitney test*) in Ad5-directed CMI responses after immunizations with Ad5 [E1-, E2b-]-CEA(6D) (22.6 ± 9.3 SEM IFN- γ secreting SFC at week 0 versus 191.1 ± 83.7 IFN- γ SFC at week 9).

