8.4.4 Safety Analysis

DLTs will be evaluated continuously in a dose level. An overall assessment of whether to de-escalate to the next dose level will be made at least 1 week after the last subject in the previous dose level has received their first injection. A dose level will be considered safe if $< 33\%$ of subjects treated at a dose level experience a DLT (i.e., 0 of 3, ≤ 1 of 6, ≤ 2 of 9, ≤ 3 of 10). Safety will be evaluated in 3 or 6 subjects at each dose level in the dose escalation component of the study. Safety will continue to be monitored among additional subjects treated at the MTD or HTD in the dose expansion component of the study. A subject will be considered evaluable for safety if treated with at least one injection. DLTs will be observed for 1 week.

Safety endpoints will be analyzed as summary statistics during treatment and/or as change scores from baseline assessments. AEs will be coded as defined in the Medical Dictionary for Regulatory Activities (MedDRA). All AEs will be recorded and tabulated following each treatment (vaccine injection). AEs will be recorded by severity, frequency, and relationship to the study intervention and will be presented by System Organ Class (SOC) designations and preferred term groupings. Information on each AE will include start date, stop date, severity, relationship, expectedness, outcome, and duration. Adverse events leading to premature discontinuation from the study intervention and serious treatment-emergent AEs will be presented either in a Table or a Listing.

In addition, overall safety will be assessed by descriptive analyses using tabulated frequencies of AEs by grade using CTCAE Version 5.0 within dose levels and for the overall study population in terms of treatment-emergent AEs, SAEs, and clinically significant changes in safety laboratory tests, physical examinations, ECGs, and vital signs.

The safety events listed in section [8.4.6.2](#) will trigger a temporary suspension of the study injections.:

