13.2 APPENDIX B: INJECTION SITE REACTIONS DIARY CARD

Please answer all questions below once per day for the first 7 days

		Day 0 (Day of Injection)	Day +1	Day +2	Day +3	Day +4	Day +5	Day +6
1. Is there redness at the injection site?	Circle: Yes / No If yes measure longest diameter in millimeters (mm)	Yes / No _____mm						
2. Is there firmness or swelling at the injection site?	Circle: Yes / No If yes measure longest diameter in millimeters (mm)	Yes / No _____mm						
3. Is there soreness at the injection site?	Circle: Yes / No If yes tell us if the soreness is mild, moderate, or severe	Yes / No Mild Moderate Severe						
4. Have you experienced pain at the injection site?	Circle: Yes / No If yes tell us if the pain is mild, moderate, or severe	Yes / No Mild Moderate Severe						
5. Have you taken any medication for	Circle: Yes / No Provide name and	Yes / No Name: _____						

		Day 0 (Day of Injection)	Day +1	Day +2	Day +3	Day +4	Day +5	Day +6
injection site pain?	dose of medication	Dose: _____						
6. Have you experienced chills?	Circle: Yes / No If yes tell us if the chills are mild, moderate, or severe	Yes / No Mild Moderate Severe						
7. Record your daily temperature (Do not drink anything within 5 minutes prior to taking your temperature)	Circle: Yes / No If your temperature is 104°F for more than 24 hours, call your study doctor	Record Temp: _____

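### The reaction diary covers the first vaccination only, so mild to moderate reactions are likely to be under-recorded at later doses and per-vaccination AE counts are not comparable

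*Combined protocol and SAP*

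**What the plan says.** Three places agree on how far the diary reaches.

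- Section 3.6 provides a "diary card with reporting fields for diameter of erythema and duration for the seven days after the first set of vaccine injections", to be reviewed at the next clinic visit and entered in the case report form.
- The study calendar (section 3.5) marks "Dispensation of Subject Diary Card" at week 0 only and "Review of Subject Diary Card" at week 3 only. Its dosing columns are weeks 0, 3, 6, 14, 22, 30, 38, 46 and 54.
- Appendix B is a single card running from Day 0 to Day +6 ("Please answer all questions below once per day for the first 7 days"), with no field for the vaccination number. Its local questions are in the singular ("Is there redness at the injection site"), although section 11.1.5.3 places the three vaccines at three sites.

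Section 1.1.4 lists treatment-emergent AEs and SAEs among the primary endpoints. Section 8.4.4 states: "All AEs will be recorded and tabulated following each treatment (vaccine injection)". Nothing in section 8 says how diary data are analysed or whether they are kept apart from unsolicited reports.

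Section 3.3 mentions a diary card within a recovery rule that applies "after each vaccination in order to receive a subsequent vaccination". It does not say that a new card is issued each time.

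**The concern.** The regimen is repeat-dose, and its overall safety is the primary objective. Section 3.6 expects local reactions to develop over several days, so a check before discharge sees only their start. At dose 1 a daily prompt captures the rest, including chills and temperature. From dose 2 on, no instrument is provided and the subject must remember at the next visit.

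A change of measurement method between dose 1 and dose 2 is confounded with vaccination number. Anyone reading AE counts by vaccination would be comparing solicited with recalled data, and the expected direction of the error is towards an apparent decline. The single-site card adds a smaller problem: even at dose 1, a reaction cannot be attributed from the card to one of the three vaccines, and these documents report clinical data for only one of them, ETBX-011.

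**Working it through.** **1. Number of vaccinations (section 3.5).** Weeks 0, 3 and 6, then 6 + 8k for k = 1 to 6, give 14, 22, 30, 38, 46 and 54. That is 3 + 6 = 9 visits and reproduces the calendar. Week 54 lies beyond 52 weeks even with the 1-week window (54 − 1 = 53), so a strict one-year limit gives 8.

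**2. Diary coverage.**
- Visits: 1/9 = 11% (1/8 = 12.5% on the strict reading).
- Injections: 3 of 9 × 3 = 27.
- Days within the 7-day windows: 7 of 9 × 7 = 63.

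These are figures for a subject who completes the schedule. Subjects who stop early, for example at progression, have fewer uncovered doses.

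**3. Recall interval without a diary.** Dose 2 to the next visit is 6 − 3 = 3 weeks. Doses 3 to 8 each have 8 weeks. Dose 9 is followed by an end-of-treatment visit within 90 days.

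**4. What the change of method could do.** The documents give no capture rate, so this is an illustration. Let p be the true reaction rate per vaccination and s the share captured without a diary, with capture at dose 1 taken as complete. For scale, p = 21/94 = 22.3%, the ETBX-011 injection-site reaction figure in section 11.1.2, which matches the printed value. The share s is assumed over 0.3 to 0.9.

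- Recorded later rate if the true rate is unchanged: p × s.
- True later rate that would look unchanged: p / s.
- Recorded later rate if the true rate doubles: 2p × s.
- Last column: the chance that 10 subjects show no more recorded reactions at a later dose than at dose 1 although the true rate has doubled. It uses exact binomials, treats doses as independent and assumes all 10 are still on treatment.

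| s | Unchanged rate recorded as | True rate that looks unchanged | Doubled rate recorded as | Chance that doubling shows no increase (n = 10) |
|---|---|---|---|---|
| 1.0 | 22.3% | 22.3% | 44.7% | 20% |
| 0.9 | 20.1% | 24.8% | 40.2% | 26% |
| 0.7 | 15.6% | 31.9% | 31.3% | 42% |
| 0.5 | 11.2% | 44.7% | 22.3% | 61% |
| 0.3 | 6.7% | 74.5% | 13.4% | 80% |

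The first row shows that ten subjects give weak information even with full capture. The lower rows show how much an uneven method takes from what is left. Any s below 1 biases in the same direction; only the amount depends on the assumption.

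The 22.3% is itself only a rough scale. It is pooled over doses of one vaccine, and its table row lists 21 events against attributions that add to 2 + 21 = 23.

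**The case against.** The case for leaving the plan alone has real substance.

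- **The dose decision does not use later diaries.** The DLT window in section 3.1.1 follows the first dose, which the card covers. A reader might infer that the MTD rests on biased data; it does not.
- **Later doses are monitored.** The calendar marks injection-site monitoring and AE collection at every dosing visit, and the sentence on self-reporting in section 3.6 is not limited to dose 1. Serious, severe or persisting reactions would be recorded, and the halting rules in section 8.4.6.2 are cumulative. This stands. What remains exposed is the milder reaction that starts and resolves at home, for which no instrument is supplied after dose 1.
- **No trend analysis is planned.** Section 8.4.4 describes summaries by organ class, term, grade and dose level, all descriptive. That is correct, but it also calls for tabulation after each injection, and that table invites the comparison.
- **The recovery rule does not need the card.** A reader might infer that the rule in section 3.3 cannot work without a diary at each dose. Recovery can be judged at the next dosing visit, and a card ending on Day +6 would not document it even at dose 1. Only the diary sentence needs reconciling.
- **Rising anti-vector immunity is not rising reactogenicity.** Section 1.2.6.2 reports "Ad5 Ab titers that were significantly increased", with means of 1:189 and 1:4767 (4767/189 = 25.2), and Ad5-directed cellular responses of 22.6 and 191.1 (191.1/22.6 = 8.5). A reader might infer that reactions will worsen. The documents do not link these measures to local reactions. The first titre is a mean over all patients and the second comes from those given three immunizations. The same trial reported self-limited site reactions and no DLT.

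Collecting solicited data around the first dose is a defensible phase 1 choice for dose finding. It serves less well the broader aim of describing the safety of a year-long regimen.

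**Conclusion.** The concern holds as a change of ascertainment after dose 1. At most 1 of 9 scheduled vaccinations (1 of 8 on the strict reading) has solicited data, while a primary endpoint is tabulated for all of them. Mild to moderate reactions after discharge are likely to be under-recorded at later doses, and a by-vaccination table could show an apparent fall when the true rate is flat or rising.

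This rests on one assumption that the documents do not quantify: that recall over 3 to 8 weeks captures fewer such reactions than a daily card. The figures above illustrate the direction and possible range and do not estimate the loss. The documents do not show that reactions worsen with repeat dosing; the point is that the plan could not reliably tell. With serious events and the DLT/MTD decision unaffected, this is a correction worth making but no obstacle to starting the trial.

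**What to change.** 1. **Section 3.6 and the calendar:** dispense the existing 7-day card at each vaccination visit, or at least at weeks 0, 3, 6 and the first booster (week 14), and review it at the next visit.
2. **Appendix B:** add a vaccination number and one entry per injection site.
3. **Section 8.4.4:** report solicited reactions by vaccination number and separately from unsolicited AEs. If the card stays at dose 1 only, state that dose 1 solicited rates will not be compared with later doses.
4. **Section 3.3:** reconcile the diary sentence with sections 3.5 and 3.6.

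The visits are already scheduled, so the cost is modest but not nil: a protocol amendment, minor CRF changes, more low-grade events recorded and some subject burden. With per-site entries, a subject who completes all nine visits would fill in 27 × 7 = 189 site-days; the four-visit minimum needs 4 × 3 × 7 = 84. The statement in item 3 alone needs no new data collection, but it removes only the misreading and leaves later reactions under-recorded.
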